(2) Construction and Multi-level Clinical Validation of Treatment Response Prediction Model

This is the core part of the study. Based on the quantified tumor immune microenvironment features output by the above model, combined with imaging data and essential clinical variables (such as TNM stage, Child-Pugh liver function classification and AFP level), a classification model will be built to predict patients' responses to four types of postoperative adjuvant therapy regimens: surgery alone, surgery combined with TACE, surgery combined with TACE plus systemic therapy, and surgery combined with systemic therapy alone. A strict hierarchical validation strategy will be adopted in this part.

Model Training Phase

Retrospective data from our center (n=1500) will be used. Inclusion criteria for patients in this phase: ① Histopathologically confirmed HCC; ② Underwent curative surgical resection; ③ Complete preoperative contrast-enhanced CT/MRI images, records of postoperative adjuvant therapy and follow-up data are available. Definition of treatment response: The primary endpoint is Relapse-Free Survival (RFS), and secondary endpoints include Overall Survival (OS) and Objective Response Rate (ORR). Multi-category machine learning algorithms (such as Gradient Boosting Decision Tree and Deep Neural Network) will be used for model training to output the most beneficial treatment regimen for each patient.

Internal Validation Phase

An independent validation set (n≈500, no overlap with the training set) will be randomly divided from the data of our center for preliminary evaluation of the model's discriminative performance and hyperparameter tuning to prevent overfitting.

External Validation Phase 1 (Retrospective Validation and Model Calibration)

Retrospective data (n=3000) will be collected from 8 to 10 medical centers nationwide. The main purposes of this phase are: ① To validate the model performance on larger and more heterogeneous external datasets; ② To calibrate or slightly optimize the model according to

validation results and finalize the predictive model.

External Validation Phase 2 (Large-scale Retrospective Validation)

The finalized model will be tested on a brand-new large-scale retrospective dataset (n=10,000) from 3 to 5 medical centers to further enhance the level of evidence and provide a solid basis for prospective studies.

(3) Study Population

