A total of 1,500 eligible surgical patients from our center will be enrolled and randomly divided into the model training set (n=1000) and internal validation set (n=500) at a ratio of 2:1, for model training, preliminary validation and optimization respectively. A total of 400 eligible patients have been enrolled so far, and the remaining 1,100 patients will be continuously recruited from the historical medical records of our center according to the inclusion and exclusion criteria.

A multi-center collaboration model will be adopted for external validation. ① External Validation

Set 1: A total of 3,000 retrospective cases from 8 to 10 domestic medical centers will be included for multi-center retrospective validation and model calibration, so as to verify the model's generalization ability across different institutions and conduct calibration or limited iterative optimization on the initial model. ② External Validation Set 2: A total of 10,000 retrospective cases from 3 to 5 large domestic medical centers will be included for the final test of the finalized model to fully evaluate its effectiveness and stability. Only forward validation will be performed on this dataset using the locked model without any parameter adjustment.

Part Two: Clinical Validation of Hepatocellular Carcinoma Adjuvant Therapy Prediction Model - Prospective Study

(1) Prospective Observational Study

A total of 1,000 eligible postoperative HCC patients will be consecutively enrolled from 10 to 15 medical centers. Preoperative imaging data, postoperative WSIs and clinical data will be collected and imported into the model to obtain predicted treatment regimens. No intervention will be implemented on actual clinical decisions in this phase. Researchers will record model prediction results and actual clinical decisions. Patients will be divided into the prediction-consistent cohort and prediction-inconsistent cohort according to whether the actual clinical decisions are consistent with model predictions. Long-term follow-up will be conducted to observe patients' actual prognosis, so as to evaluate the consistency between model predictions and actual outcomes, as well as the model's performance degradation in real-world settings.

(2) Study Population

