3.4.1 Sample Size for Retrospective Study Phase

(1) Sample Size for Model Training and Validation: Training Set ($n = 1,000$) and Internal Validation Set ($n = 500$)

Estimation Basis: The sample size of this phase follows empirical rules of machine learning and feasibility principles. Complex deep learning models for WSIs require a large amount of annotated data to avoid overfitting. Empirical experience shows that 1,000 to 5,000 samples are generally required for each category. This study targets four categories of treatment response classification. A sample size of 1,000 is set to balance model performance and data collection feasibility, which is consistent with the sample size of existing top-tier multimodal AI studies. The size of the internal validation set generally accounts for 20%–30% of the training set. A total of 500 samples can estimate model performance indicators (such as AUC) with a small standard error and meet the requirements of hyperparameter tuning.

(2) External Validation Set 1 ($n = 3,000$)

Estimation Basis: This phase is used for preliminary evaluation of model calibration and generalization ability, and a sufficient sample size is required to detect clinically significant declines in model performance.

a sample size of 3,000 provides sufficient statistical power to support subgroup analysis and subsequent fine-tuning of the model.

(3) External Validation Set 2 ($n = 10,000$)

Estimation Basis: This phase is for the final test of the locked model, and a high-precision estimation of performance indicators (such as AUC) is required. The sample size is calculated reversely according to the width of the AUC confidence interval.

Given $AUC = 0.80$ and the target 95% confidence interval width ≤ 0.04 (i.e., ± 0.02),

approximately 8,600 cases are required according to calculations using PASS software. A total of 10,000 cases are set to reserve sufficient margin and ensure high credibility of the results.

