3.5 Bias Control and Fairness

A multi-level and systematic strategy is adopted to strictly control various potential biases in the study and ensure the scientificity and reliability of research results.

Bias control in study design phase: Standardized inclusion and exclusion criteria are formulated to control selection bias. In multi-center studies, all centers are required to adopt a unified patient screening process. Selection bias is assessed by comparing the basic characteristics of enrolled and unenrolled patients. For the prospective interventional study, central randomization (block randomization stratified by center) is used to assign patients to the AI-assisted decision-making group or standard treatment group to ensure balanced baseline characteristics between groups.

Bias control in data collection and processing phase: Strict blinding principles are implemented to reduce information bias and measurement bias. For pathological image annotation, at least two senior pathologists conduct independent annotations without access to any clinical outcomes of patients, and discrepancies are arbitrated by a third expert to establish high-quality gold standards. During model development, algorithm developers are prohibited from accessing data of subsequent validation sets to avoid overfitting caused by manual tuning. An independent clinical endpoint adjudication committee is established in the endpoint evaluation phase. Committee members are blinded to patient grouping information and AI prediction results, and judge tumor recurrence and survival events objectively according to established criteria to minimize assessment bias.

Bias control in algorithm development and validation phase for AI-specific biases: For spectrum bias, slide images scanned by different devices and stained with different procedures from multiple medical centers are collected. Color normalization techniques (such as the Macenko method) are adopted in the preprocessing phase to reduce the impact of staining differences. Multi-center and large-sample external validation is conducted to evaluate and correct the performance differences of the model across different populations and devices so as to control measurement bias. In addition to dividing independent validation sets, regularization and Dropout technologies are applied to prevent overfitting. Cross-validation and Bootstrap sampling results are used when evaluating model performance.

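### The 500 internal validation patients are used both to tune the model and to estimate its discrimination, so the internal AUC is optimistic, and the stated rationale and training numbers do not agree

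*Protocol*

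**What the plan says.** Protocol section 3.1, Part One (3), Definition and Source of Datasets, has the 1,500 own-centre patients "randomly divided into the model training set (n=1000) and internal validation set (n=500) at a ratio of 2:1". The first set is for training, the second for preliminary validation and optimisation.

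Section 3.1, Part One (2), Internal Validation Phase, calls the 500 independent, says they share no patients with the training set, and uses them for preliminary evaluation of "discriminative performance and hyperparameter tuning to prevent overfitting". Section 3.4.1 (1) repeats both uses: the 500 are to give an AUC with a small standard error and also to serve hyperparameter tuning. Its rule of thumb is "The size of the internal validation set generally accounts for 20%–30% of the training set".

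Two other places give a different training number. Section 3.1, Part One (1), Development and Training Phase, names all 1,500 own-centre cases, with public data, as the training set of the microenvironment model. Part One (2), Model Training Phase, gives n=1500 for the treatment-response model, which takes the microenvironment model's output as input.

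Section 3.5 adds that "algorithm developers are prohibited from accessing data of subsequent validation sets to avoid overfitting caused by manual tuning" and that "Cross-validation and Bootstrap sampling results are used when evaluating model performance". External Validation Set 2 (n=10,000) is reserved for the locked model, with no parameter adjustment.

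**The concern.** Choosing the best of several settings on a set of patients selects partly for chance in those patients. The winner's AUC in the same patients is therefore too high on average, and calling the set independent invites the reader to take it as a clean estimate. The protocol describes no other untouched internal set, and it does not tie the cross-validation of section 3.5 to tuning.

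Two further things weaken the internal result. The rule cited for the size of the set does not lead to 500. And if the microenvironment model really is trained on all 1,500, the 500 are not independent of the inputs to the response model.

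At stake is how far the internal AUC can be trusted when a model is carried into External Validation Set 1. The final performance claim is not at stake.

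**Working it through.** **1. The split.** 1,500 × 2/3 = 1,000 and 1,500 / 3 = 500, so the plan's figures reproduce.

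**2. The 20%–30% rule.** 500 / 1,000 = 50% of the training set. Read as a share of all patients, 500 / 1,500 = 33.3%, still above 30%. Applied to 1,500 patients, the rule gives:
- at 20%: 1,500 / 1.2 = 1,250 for training and 250 for validation;
- at 30%: 1,500 / 1.3 = 1,154 for training and 346 for validation.

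**3. Precision of an AUC from 500 patients.** AUC A = 0.80 is borrowed from the protocol's calculation for External Validation Set 2. The share of positives is assumed. The Hanley-McNeil formula is

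SE² = [A(1−A) + (n1−1)(Q1−A²) + (n0−1)(Q2−A²)] / (n1·n0),

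with Q1 = A/(2−A) = 0.6667, Q2 = 2A²/(1+A) = 0.7111 and A² = 0.64.
- 50% positives (250/250): SE² = (0.16 + 6.64 + 17.71) / 62,500, SE = 0.0198, 95% half-width 1.96 × 0.0198 = 0.039.
- 35% (175/325): SE² = (0.16 + 4.64 + 23.04) / 56,875, SE = 0.0221, half-width 0.043.
- 40%: SE = 0.0211.
- 25%: SE = 0.0253, half-width 0.050.

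**4. Optimism from tuning and evaluating on the same 500.** If K settings have the same true AUC and their estimates correlate at ρ, the best one is too high on average by

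SE × √(1−ρ) × E[maximum of K standard normals].

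The expected maximum, found by simulation, is about 1.54 for K = 10 and 2.25 for K = 50. K, ρ and the share of positives are assumptions; the documents give none of them. Each range runs from 40% to 25% positives.

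| K | ρ = 0.9 | ρ = 0.8 | ρ = 0.5 |
|---|---|---|---|
| 10 | +0.010 to +0.012 | +0.014 to +0.018 | +0.023 to +0.028 |
| 50 | +0.015 to +0.018 | +0.021 to +0.026 | +0.034 to +0.040 |

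Lowest cell: 0.0211 × √0.1 × 1.54 = 0.010. Highest: 0.0253 × √0.5 × 2.25 = 0.040.

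**5. Would a smaller validation set help?** No. At 25% positives the SE is 0.0327 with 300 patients against 0.0253 with 500. Following the 20%–30% rule would make the internal AUC less precise and leave the double use in place.

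**6. The training numbers side by side.** Part One (1) has 1,500 as the training set. Part One (2) has 1,500 under Model Training Phase, then about 500 drawn from the same centre without overlap. The dataset definition in Part One (3) has 1,000 and 500. In Part One (2), 1,500 could be read as the pool before the split. Part One (1) does not allow that reading, because it calls the 1,500 the training set.

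**The case against.** The strongest reply is that tuning on a validation set and reporting from an untouched test set is ordinary practice, and that the protocol does this. The internal result is labelled preliminary, External Validation Set 2 is tested with a locked model, and no threshold, sample size or clinical step is tied to the internal AUC. This stands, and it limits the point to the internal figure. It does not justify calling the 500 independent while they choose the settings.

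A reader might infer three stronger things that the documents do not support.
- **That a third of the data is lost to training.** The dataset definition suggests it, but two other places give 1,500 for training and nothing forbids a final refit on all 1,500. What is established is an unreconciled conflict.
- **That tuning on the 500 breaks the access rule in section 3.5.** That rule covers subsequent validation sets during model development. It can be read as covering sets later than the current stage, which permits tuning on the internal set. The wording needs clarifying, but no breach is shown.
- **That the 20%–30% rule is binding.** It is worded as what is generally done, and the next sentence offers a small standard error as a separate reason for 500. The rule fails as a justification, but 500 is not thereby the wrong number.

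Section 3.5 does plan cross-validation and bootstrap, in addition to the split. The detail may sit in an SAP. But the protocol itself gives the 500 the tuning role, and bootstrapping the tuned model on those same 500 would leave the optimism in.

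**Conclusion.** The point holds as a minor one. If the plan is followed as written, the internal AUC is biased upwards. The direction follows from the double use. The size, about +0.01 to +0.04, is illustrative: it rests on an AUC of 0.80, 10 to 50 settings, correlation 0.5 to 0.9, 25% to 40% positives and settings of equal true merit. Where settings truly differ, the optimism is generally smaller. The calculation also uses a two-class AUC, whereas section 3.8 names macro-average AUC and weighted F1 as the main indicators.

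The optimism should not be set against the ±0.02 required of External Validation Set 2 as if it threatened that result, because that set is untouched by the tuning.

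Two textual errors stand whatever is assumed: 500 is 50% of 1,000 and not 20%–30%, and the training numbers in section 3.1 disagree.

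**What to change.** - **Tuning.** Tune by cross-validation inside the 1,000 training patients only, using the cross-validation already named in section 3.5. Evaluate the chosen model once on the untouched 500. The final model may then be refitted on all 1,500 before External Validation Set 1. If the 500 are kept for tuning, label their AUC a tuning-stage figure and not independent validation.
- **Microenvironment model.** Train it without the 500 as well, or state that the 500 are not independent of it.
- **Section 3.4.1.** Replace the 20%–30% justification with the precision that 500 gives: about ±0.04 at AUC 0.80 with 35% to 50% positives.
- **Section 3.1.** Reconcile 1,500 with 1,000 and 500 in the three places.
- **Section 3.5.** State that External Validation Set 1 is open to developers for calibration, and that its validation result is the one obtained before any calibration or optimisation.

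**Cost.** No extra patients or data are needed, only wording, computing time and a slightly less favourable internal AUC. With five folds, tuning K settings takes 5K fits in place of K. Nested cross-validation on all 1,500 is an option if computing allows. With five outer and five inner folds it needs about 25K fits plus 5K to tune the final model, roughly 30 times a single split. The microenvironment model would also have to be refitted in each outer fold for the folds to be independent.

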Research Title: Construction and Clinical Validation of a Predictive
Model for Postoperative Adjuvant Therapy in Hepatocellular Carcinoma
Based on Whole-Slide Digital Pathological Images and Deep Learning

NCT Number: NCT07417800

Document date: 2025/10/24

Research Protocol

Study Background

Hepatocellular Carcinoma (HCC) is one of the most common malignant tumors worldwide, ranking sixth in incidence and third in mortality globally, causing approximately 480,000 deaths each year. China accounts for more than 45% of global HCC cases, resulting in an extremely heavy disease burden. Curative surgical resection is the primary approach to achieve long-term survival for patients with early-stage HCC. However, the postoperative recurrence rate reaches 50%–70% within five years after surgery, which seriously impairs patient prognosis. Postoperative adjuvant therapy has become a key strategy to delay tumor recurrence and improve survival outcomes. Transarterial Chemoembolization (TACE) and Tyrosine Kinase Inhibitors (TKIs), such as sorafenib and lenvatinib, are widely applied for patients at high recurrence risk after surgery.

Nevertheless, both treatment modalities have notable limitations. The objective response rate of TACE is merely 50%–60%; a considerable number of patients fail to benefit from this therapy and may suffer from treatment-induced liver function injury. Although TKIs can prolong recurrence-free survival (RFS) by 3 to 5 months in high-risk postoperative HCC patients, the treatment response rate is less than 20% in unselected populations. Additionally, the incidence of Grade 3–4 adverse events including hypertension, hand-foot skin reaction and proteinuria exceeds 50%, leading to treatment discontinuation in around 20% of patients due to intolerable toxicities. Currently, there is a lack of efficient and reliable biomarker systems to identify patients who may benefit from treatment. Clinical treatment decisions still rely on empirical judgment based on conventional pathological features such as tumor size and vascular invasion, resulting in insufficient individualized treatment, wasted medical resources and additional treatment burdens on patients.

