3.4.2 Sample Size for Prospective Study Phase

(1) Sample Size for Prospective Observational Validation ($n = 1,000$)

Estimation Basis: This phase evaluates the correlation strength between model predictions and real clinical prognosis (C-index) using sample size formulas for survival analysis. Relapse-Free Survival (RFS) is taken as the primary endpoint.

Assuming the 12-month RFS rate of the control group is 60% and the corresponding HR of the model-consistent group is 0.7, a total of 256 events are expected. Simulated by PASS 2021 software, more than 300 events can be observed in 1,000 cases within a 24-month study period (12 months for enrollment + 12 months for follow-up), which meets the requirements of statistical power and supports stratified analysis.

(2) Sample Size for Prospective Interventional Study

Estimation Basis: This phase is a Randomized Controlled Trial (RCT) with strictly calculated sample size, taking RFS as the primary endpoint.

Sample size formula for Log-Rank test is adopted with the following parameter settings: Baseline event rate: The 12-month RFS rate of the standard treatment group (Arm B) is 65%. Effect size: The 12-month RFS rate of the AI-assisted decision-making group (Arm A) is increased by an absolute value of 10% (up to 75%), corresponding to $HR = 0.67$. Significance level (α): 0.05. Statistical power ($1-\beta$): 80% (conventional standard for RCT). Accrual time: 18 months. Follow-up time: 12 months. Dropout rate: 10%.

Calculated by PASS 2021 software, a total of 200 events are required. Considering the dropout rate, the total required sample size is 600 cases (300 cases in each group). This sample size can detect the clinical difference corresponding to $HR = 0.67$ and meet the power requirements under follow-up and dropout conditions.

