Fairness assessment: Comprehensive fairness evaluation is carried out to analyze whether there are significant differences in model performance across subgroups divided by demographic characteristics (gender, age) and clinical characteristics (tumor stage, etiology, liver function classification). Core evaluation indicators include inter-group AUC difference, balanced odds and fairness metrics for sensitive attributes. If performance discrimination of the model is found in specific subgroups, algorithm correction will be performed to ensure the fairness of algorithm decisions. All fairness evaluation results will be fully disclosed in the research report.

Bias control in statistical analysis phase: Multivariate Cox regression model and Logistic regression model are used to adjust for known prognostic factors (such as TNM stage, vascular invasion and AFP level) to accurately estimate the independent predictive efficacy of the AI model and control potential residual confounding bias.

3.6 Data Governance System (Data Collection, Transmission, Storage Security Control; Full-chain Data Recording)

A sound data governance system is established to ensure the quality, security and compliance of data throughout the research process, covering all links including data collection, transmission, storage, processing, analysis and archiving, forming a complete data management closed loop.

Standardized data collection: Detailed Standard Operating Procedures (SOPs) for data collection are formulated to clarify the definition, format and collection specifications of all types of data. Structured electronic Case Report Forms (eCRFs) are used for clinical data collection with built-in logic verification and range check functions to ensure the accuracy and completeness of data collection. Pathological image data collection follows digital scanning standards with a unified scanning resolution of 0.25 μ m/pixel and file format of SVS. Equipment calibration and quality control tests are conducted before each batch of scanning. Laboratory test data are directly collected by docking with the Laboratory Information System (LIS) to avoid manual transcription errors.

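### The observational phase compares RFS between pooled consistent and inconsistent cohorts, so regimen-related prognosis can move the HR away from 1 in either direction when following the model has no benefit

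*Protocol*

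**What the plan says.** Protocol 3.1, Part Two (1), leaves care to the physician: "No intervention will be implemented on actual clinical decisions in this phase". The cohorts are formed afterwards: "Patients will be divided into the prediction-consistent cohort and prediction-inconsistent cohort according to whether the actual clinical decisions are consistent with model predictions". The model chooses among four options (3.1, Part One (2)): "surgery alone, surgery combined with TACE, surgery combined with TACE plus systemic therapy, and surgery combined with systemic therapy alone". All four are pooled on each side of the split.

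Section 3.4.2 (1) takes RFS as primary endpoint, assumes 12-month RFS of 60% in the control group, and states that "the corresponding HR of the model-consistent group is 0.7", leading to 256 events. It also names the C-index as what the phase evaluates.

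Sections 3.3 and 3.8 compare groups with a log-rank test. Section 3.5 adds multivariable models to "adjust for known prognostic factors (such as TNM stage, vascular invasion and AFP level"), and 3.8 gives age, gender and TNM stage as examples. Neither list names the recommended regimen, the regimen received, or a propensity for either.

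On how regimens are chosen, the Study Background says that TACE and TKIs "are widely applied for patients at high recurrence risk after surgery", and: "Clinical treatment decisions still rely on empirical judgment based on conventional pathological features such as tumor size and vascular invasion".

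**The concern.** Agreement with the model is not assigned; it results from two choices that both depend on prognosis. Adjuvant treatment goes to patients judged to be at high risk, so the regimen received marks risk. The recommendation is computed from TNM stage, AFP, imaging and slide features, and the Study Background credits slide-based models with an AUC of 0.82 for recurrence, so the recommendation marks risk too.

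If agreement is more frequent for the regimen typical of low-risk patients, the consistent cohort is enriched for patients who would do well anyway. If it is more frequent for the regimens of high-risk patients, the reverse happens. The pooled HR then mixes any benefit of following the model with a difference in case mix. An HR near the planned 0.7 could be read as validation when concordance does nothing, and a useful model could look useless.

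**Working it through.** **1. The plan's own figure.** Inputs from 3.4.2 and 3.8: HR 0.7, two-sided alpha 0.05. Power is not stated for this phase; 80% is assumed, as for the randomised trial. Freedman's formula gives (1.960 + 0.842)² × (1.7/0.3)² = 7.849 × 32.11 = 252.04, so 253 events against the stated 256. Schoenfeld at 1:1 gives 247, and at a 40:60 split 258. The 256 is reproduced. Under exponential RFS with 12 + 12 months, 1,000 patients give 447 to 495 events (403 to 445 with 10% loss), in line with the stated figure of more than 300. The event count is not the problem.

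**2. Prognosis follows the recommendation.** Assume half the patients are recommended surgery alone, concordance has no effect, and 12-month RFS is 75% in that half and 45% in the other. With agreement of 80% and 50%:
- Consistent: 0.40 low-risk and 0.25 high-risk, so RFS = (0.40 × 75 + 0.25 × 45)/0.65 = 63.5%.
- Inconsistent: 0.10 and 0.25, so RFS = (0.10 × 75 + 0.25 × 45)/0.35 = 53.6%.
- Approximate HR = ln(0.635)/ln(0.536) = 0.73.

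The same arithmetic for other assumed values:

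| Agreement | 12-month RFS | HR |
|---|---|---|
| 80/40 | 75/45 | 0.67 |
| 80/50 | 75/45 | 0.73 |
| 70/50 | 75/45 | 0.82 |
| 80/50 | 75/60 | 0.83 |
| 70/50 | 75/60 | 0.89 |
| 60/50 | 75/45 | 0.91 |
| 50/70 (reversed) | 75/45 | 1.23 |

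Simulation with 1,000 patients agrees within its error. It finds p < 0.05 in 92% of runs for 80/50 and 65% for 70/50 (both with RFS 75/45), in 45% for 80/50 with RFS 75/60, and in 22% for 60/50. The 75/45 runs have about 520 events, somewhat more than step 1 expects, so these percentages are a little high.

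**3. Prognosis follows the regimen received.** Assume a care mix of 50/25/10/15% (surgery alone, TACE, TACE plus systemic, systemic), prognostic hazards of 1/1.5/2.5/2, recommendations unrelated to the patient, and no treatment effect. Crude HR:
- uniform recommendations: 1.01
- recommendations in the care mix: 0.79
- 70% surgery alone: 0.68
- 90% surgery alone: 0.60
- 10% surgery alone: 1.16

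**4. Does the planned adjustment help?** The log-rank test has none. For the Cox model, take a 1.9-fold crude prognostic gap and 90% surgery-alone recommendations (crude HR 0.57 to 0.58). If the covariates capture 25, 50, 75 or 100% of the prognostic variance that drives treatment choice, the adjusted HR is 0.63, 0.72, 0.84 or 1.00. Adjustment shrinks the bias and removes it only in the last case.

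**5. Which analysis removes it?** Stratifying by recommended regimen gives about 1.0 in step 2, but leaves about 0.76 (care mix) and 0.64 (70% surgery alone) in step 3. Stratifying by received regimen gives about 1.0 in step 3, but leaves 0.86 in the 80/40 case of step 2; that value also depends on which regimen the disagreeing patients receive. A Cox model with main effects for both regimens gives 0.98 to 1.01 in every scenario tried, within simulation error.

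**The case against.** The best defence has four parts.

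- **Purpose.** Section 3.1 describes this phase as checking predictions against outcomes and looking for performance degradation, and evidence of clinical utility is left to the randomised trial. No passage makes that trial conditional on this HR. This stands, and it limits the severity. But 3.4.2 still sizes the phase on the concordance contrast, so the contrast is more than a side description.
- **Adjustment.** Both covariate lists are open-ended, and tumour size and number, differentiation, vascular invasion and PIVKA-II are collected. A separate analysis plan may name more. This stands in part: prognostic covariates help as far as they capture what drives treatment choice, but the protocol also uses an unadjusted log-rank test and attaches the HR to the pooled split.
- **Magnitude.** Agreement rates and RFS by regimen are assumptions. An HR near 0.7 in step 2 needs about 30 points on both gaps; smaller gaps give 0.83 to 0.91. The protocol also says "Assuming the 12-month RFS rate of the control group is 60" (per cent), which is the control-group rate, whereas the 75/45 split averages 60% over the whole cohort. Both remarks stand.
- **A worthless model.** A reader might infer that any model without value will produce the expected 0.7. The documents do not support that. Uniform recommendations give about 1.0, and a model that mostly recommends adjuvant regimens gives an HR above 1. The model in step 2 is strongly prognostic; what it lacks is any benefit from being followed.

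**Conclusion.** The point holds as a should-fix. The pooled contrast in 3.1, with the HR of 0.7 in 3.4.2, cannot separate a benefit of following the model from differing agreement across prognostically different regimens. With no true benefit, the crude HR is about 0.66 to 0.84 for most pairings of a 20 to 40 point agreement gap with a 15 to 30 point RFS gap, and 0.89 when both gaps are smallest. It is near 1.0 for uniform recommendations unrelated to the patient and above 1 when the agreement pattern is reversed. These sizes rest on assumed agreement rates, care mixes and RFS by regimen. That regimens carry prognosis rests on the protocol's own Background and model description.

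Three stronger readings are not supported: that the 256 events are wrong (they reproduce), that the planned 0.7 is itself an artefact (it is only within reach of one), and that the randomised trial is compromised (its groups are formed by randomisation, not by agreement).

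**What to change.** In Protocol 3.1 Part Two (1), 3.4.2 (1) and 3.8:

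- Make the primary consistent-versus-inconsistent analysis a Cox model with main effects for both the recommended and the received regimen, plus the prognostic covariates already collected. The concordance term is then a contrast within the interaction of the two regimens.
- Report the HR by recommended regimen beside it. Within one recommendation, concordance is the same thing as the regimen received, so these HRs need the same caution about treatment selection.
- State that the pooled log-rank test and crude HR are descriptive and are not evidence that following the model improves RFS.
- Do not rely on stratifying by recommended regimen alone (step 5).

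The cost is mainly wording, because recommendation, treatment and covariates are already recorded. The interval will be wider, so the power statement in 3.4.2 should be rechecked, and sparse regimens may need merging. If nearly all recommendations are for one regimen, the concordance term becomes hard or impossible to estimate. Residual confounding by unmeasured risk remains and should be acknowledged.
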